4 INVESTIGATIONAL PLAN

4.1 Overall Study Design and Plan

This is a Phase 3, double-blind, placebo-controlled, randomized, 2-arm study evaluating the efficacy and safety of the combination of navitoclax and ruxolitinib compared to ruxolitinib, in subjects with intermediate-2 or high-risk MF. The target population comprises adult subjects with MF who have not been previously treated with JAK2 inhibitor therapy with measurable splenomegaly and are not candidates for allogeneic-stem cell transplantation.

Approximately 230 subjects will be enrolled. Subjects will be randomized in a 1:1 ratio to one of the following treatment arms, with stratification factors of intermediate-2 versus high risk (Dynamic International Prognostic Scoring System Plus [DIPSS+])¹¹ and platelet count $\leq 200 \times 10^9/L$ versus $> 200 \times 10^9/L$:

- **Arm A – Experimental group:** navitoclax + ruxolitinib
- **Arm B – Control group:** placebo to match navitoclax + ruxolitinib

Dosing of study drugs:

- Navitoclax/placebo:
 - Platelet count $> 150 \times 10^9/L$: 200 mg once daily starting dose
 - Platelet count $\leq 150 \times 10^9/L$: 100 mg once daily starting dose; escalate to 200 mg once daily after ≥ 7 days, if tolerable (platelets $\geq 75 \times 10^9/L$).
 - After the Week 25 Day 1 visit, dose may be increased to 300 mg once daily at the discretion of the investigator based on platelet count for subjects with sub-optimal spleen response defined as failure to achieve a spleen volume reduction of at least 10%.
- Ruxolitinib (administered per USPI/SmPC/local prescribing guidance):
 - Platelet count $> 200 \times 10^9/L$: 20 mg twice daily starting dose
 - Platelet count $100 \times 10^9/L$ to $200 \times 10^9/L$: 15 mg twice daily starting dose.
 - Ruxolitinib dose adjustment in subjects with hepatic or renal impairment should be determined per local label/prescribing guidance.

Ruxolitinib and navitoclax/placebo will be administered beginning on Day 1 at the individualized starting dose based on baseline platelet counts determined within 24 hours prior to the first dose. The starting dose of ruxolitinib may be adjusted at the discretion of the investigator, as medically appropriate in consultation with the AbbVie Therapeutic Area Medical Director/Scientific Director (TA MD/SD), with subsequent increase in dose as described in [Table 1](#). Ruxolitinib and navitoclax/placebo dose reductions are permissible, as needed, for management of toxicities ([Section 6.2](#)).

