6.2 Toxicity Management

All subjects should be monitored according to the Activity Schedule in [Appendix D](#) for new-onset non-hematologic toxicity and renal toxicities, with dose delay or reduction as appropriate.

Navitoclax/Placebo

Navitoclax may be associated with cytopenias, notably thrombocytopenia, based on observations made of subjects during previous clinical trials in other indications and in the ongoing Study M16-109.

The guidelines noted below should be implemented for appropriate dosing and management of all subjects for safety. If additional dose reductions or modifications that are thought to be necessary by the investigator, a discussion with the AbbVie TA MD/SD is required.

- If a navitoclax/placebo interruption is necessary, navitoclax/placebo may be reintroduced at the same or lower dose based on the guidance below and in [Table 1](#).
 - Current dose level 200 mg once daily; reduce to 100 mg once daily, then 50 mg once daily
 - Current dose; 100 mg once daily; reduce to 50 mg once daily.
- The same navitoclax/placebo dose level shall not be attempted more than twice consecutively without prior approval from the AbbVie TA MD/SD.
- Intermediate dose levels of navitoclax/placebo (e.g., 150 mg once daily) may be administered for moderate dose adjustments.

Ruxolitinib

For ruxolitinib, in addition to the dose modification guidelines provided below and in [Table 1](#), the local, approved product label should be referenced for drug-drug interactions, precautions, monitoring, and dose adjustment guidelines for subjects with hepatic or renal impairment and all hematological and non-hematological toxicities.

For subjects who require interruption of ruxolitinib per the label but are considered to be at increased risk for exacerbation of splenomegaly and significant symptoms, ruxolitinib dose can be tapered by the Investigator in consultation with the AbbVie TA MD/SD followed by interruption.

Decisions regarding continued dosing, including the navitoclax/placebo or ruxolitinib dose level to be administered, for individual subjects will be medically managed by the investigator and consultation with the AbbVie TA MD/SD is recommended. Dosing interruptions greater than 28 days or additional dose modifications must be discussed with the AbbVie TA MD/SD.

Management of Thrombocytopenia and Bleeding Events

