- A platelet count obtained approximately 24 hours (± 1 hour) post transfusion.

Management of Neutropenia

There is a potential for clinically significant neutropenia given the toxicity profiles of both ruxolitinib and navitoclax. The management of neutropenia guidelines, as listed in [Table 1](#) and below, should be implemented for all subjects unless previously discussed and approved with the AbbVie TA MD/SD.

- For Grade 3 neutropenia in addition to interruption as listed in [Table 1](#), support with G-CSF and/or prophylaxis with antibiotics may be considered at the discretion of the investigator.
- For Grade 4 neutropenia in addition to interruption as listed in [Table 1](#), support with G-CSF and/or prophylaxis with antibiotics may be considered at the discretion of the Investigator. If, in the opinion of the investigator, ruxolitinib dose can be resumed prior to recovery of ANC $\geq 1.0 \times 10^9/L$ or needs a dose reduction, consultation with the AbbVie TA MD/SD is necessary.

At any time during the study, if the subject presents with febrile neutropenia, navitoclax/placebo and ruxolitinib, if applicable, should be interrupted until resolution of the fever or infection.

Table 1. Dose Adjustment Guidelines for Thrombocytopenia and Neutropenia

 • After navitoclax/placebo and/or ruxolitinib dose modification, platelet counts should be rechecked approximately 7 days or sooner as clinically applicable until at least 2 consecutive laboratory values indicate stable platelet count. • If treatment is interrupted for platelet count $< 50 \times 10^9/L$, recheck platelets approximately every 2 to 3 days until recovery of platelets to $\geq 50 \times 10^9/L$. • Navitoclax/Placebo Dose levels for daily dosing: 200 mg, 150 mg, 100 mg, 75 mg, or 50 mg. 		
Hematology Results	Navitoclax/Placebo	Ruxolitinib per approved local label
Dose Modification for Thrombocytopenia		

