Platelet counts $\geq 125 \times 10^9/L$	
 • Maintain dose if current navitoclax/placebo dose is 200 mg QD. • Increase dose by one dose level if current navitoclax/placebo dose is ≤ 150 mg QD and has been administered for at least 7 days without any dose modification or interruption. 	
 • Increase dose to the label recommended dose for subjects who received lower starting dose of ruxolitinib than the label recommended dose if platelet counts are stable and current dose of ruxolitinib has been administered for at least 7 days without any dose modification or interruption.
Platelet counts $\geq 100 \times 10^9/L$ to $< 125 \times 10^9/L$	
 • Maintain dose if current navitoclax/placebo dose is ≥ 150 mg QD. • Increase dose by one dose level if current navitoclax/placebo dose is ≤ 100 mg QD and has been administered for at least 7 days without any dose modification or interruption. 	
 • Maintain current ruxolitinib dose if receiving ≤ 15 mg twice daily. • Reduce dose to one dose level lower twice daily if current ruxolitinib dose ≥ 20 mg twice daily.
Platelet counts $\geq 75 \times 10^9/L$ to $< 100 \times 10^9/L$	
 • Maintain dose if current navitoclax/placebo dose is ≥ 150 mg QD. • Increase dose by one dose level if current navitoclax/placebo dose is ≤ 100 mg QD and has been administered for at least 7 days without any dose modification or interruption. 	
 • Maintain current ruxolitinib dose if receiving ≤ 10 mg twice daily. • Reduce dose to 10 mg twice daily if current ruxolitinib dose ≥ 15 mg twice daily.

 • After navitoclax/placebo and/or ruxolitinib dose modification, platelet counts should be rechecked approximately 7 days or sooner as clinically applicable until at least 2 consecutive laboratory values indicate stable platelet count. • If treatment is interrupted for platelet count $< 50 \times 10^9/L$, recheck platelets approximately every 2 to 3 days until recovery of platelets to $\geq 50 \times 10^9/L$. • Navitoclax/Placebo Dose levels for daily dosing: 200 mg, 150 mg, 100 mg, 75 mg, or 50 mg. 		
Hematology Results	Navitoclax/Placebo	Ruxolitinib per approved local label

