Platelet counts $\geq 50 \times 10^9/L$ to $< 75 \times 10^9/L$	
 • Reduce dose to one dose level lower. • Maintain dose if current navitoclax/placebo dose is 50 mg QD and counts are stable and no risk for bleeding per investigator discretion. • Interrupt dosing if current navitoclax/placebo dose is 50 mg QD and platelet counts are not stable and there is a risk for bleeding. 	
 • Reduce dose to 5 mg twice daily.
Platelet counts $< 50 \times 10^9/L$	
 • Interrupt dosing and resume at one dose level lower than prior to interruption once platelet counts recover to $\geq 50 \times 10^9/L$. 	
 • Interrupt per local label. May taper if high risk for exacerbation in discussion with TA MD/SD. • Resume at same or lower dose once platelet counts recover $\geq 50 \times 10^9/L$.
Dose Modification for Neutropenia		
Absolute neutrophil count (ANC) $< 1.0 \times 10^9/L$ to $0.5 \times 10^9/L$	
 • Interrupt dosing and monitor hematology labs at least weekly until ANC $\geq 1.0 \times 10^9/L$. • Resume at one dose level lower than prior to interruption once ANC recover $\geq 1.0 \times 10^9/L$. 	
 • Maintain current dose or interrupt per local label if at risk for infection per investigator discretion.
Absolute neutrophil count (ANC) $< 0.5 \times 10^9/L$	
 • Interrupt dosing and monitor hematology labs at least weekly or often as needed until ANC $\geq 1.0 \times 10^9/L$. • Resume at one dose level lower than prior to interruption once ANC recover $\geq 1.0 \times 10^9/L$. 	
 • Interrupt per local label. May taper if high risk for exacerbation in discussion with TA MD/SD. • Resume at same or lower dose.

Management of Infections

Subjects who develop clinically significant infections should have navitoclax/placebo and ruxolitinib interrupted and restart study drug treatment when signs or symptoms of infection have resolved.

If clinically indicated, anti-infective prophylaxis should be implemented at the investigator's discretion, including appropriate prophylaxis for viral, fungal, bacterial, or *Pneumocystis jiroveci* pneumonia infections with close monitoring as there is a potential for drug-drug interactions.

Management of Other Toxicities

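### Protocol Sections 4.1/4.2 and Table 1 give different escalation rules for subjects who start navitoclax/placebo at 100 mg, and the restart steps in Section 6.2 only partly match Table 1

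*Protocol*

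**What the plan says.** Platelet counts below are in units of 10⁹/L.

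**Escalation from the 100 mg start.** For subjects with a baseline platelet count of 150 or less, Protocol Section 4.1 gives "100 mg once daily starting dose; escalate to 200 mg once daily after" at least 7 days, provided platelets are at least 75. Section 4.2 repeats the move to 200 mg on the same platelet condition.

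Table 1 (Section 6.2) sets out "Navitoclax/Placebo Dose levels for daily dosing: 200 mg, 150 mg, 100 mg, 75 mg, or 50 mg". For platelets of 75 to < 100 and of 100 to < 125 it says "Increase dose by one dose level if current navitoclax/placebo dose is" 100 mg or less and has been given unchanged for at least 7 days. In both rows a dose of 150 mg or more is maintained. At 125 or above, a dose of 150 mg or less goes up one level and 200 mg is maintained.

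**Restart and reduction.** The Section 6.2 text says that after an interruption "navitoclax/placebo may be reintroduced at the same or lower dose based on the guidance below and in" Table 1. Beneath that it lists "Current dose level 200 mg once daily; reduce to 100 mg once daily, then 50 mg once daily" and "Current dose; 100 mg once daily; reduce to 50 mg once daily". A separate bullet permits intermediate doses, with 150 mg as the example, for moderate adjustments. The thrombocytopenia paragraph of Section 6.2 directs sites to Table 1 unless the sponsor's medical director has agreed otherwise. Table 1 says "Reduce dose to one dose level lower" at platelets 50 to < 75. Below 50 it calls for interruption and then resumption one level lower.

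**Highest dose.** After the Week 25 Day 1 visit, the "dose may be increased to 300 mg once daily at the discretion of the investigator" for subjects with a poor spleen response (Section 4.1).

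**The concern.** A subject who has taken 100 mg for a week with platelets of, say, 80 or 110 satisfies the condition in Section 4.1 and the condition in Table 1 on the same day. The two passages then name different next doses, and neither refers to the other for this step.

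The subjects concerned are those for whom the sponsor chose the lower start in order to limit thrombocytopenia (Section 4.2), which Section 2.2 calls the main dose-limiting toxicity. If sites read different passages, exposure in this group may vary for reasons unrelated to the patient.

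There are also two reporting consequences. SAP Section 6.0 divides the observed dose intensity by a planned one without saying which protocol rule sets the plan. SAP Appendix A counts subjects given an incorrect dose, which presupposes a single correct dose.

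**Working it through.** No sample size, power or alpha figure is involved. The check applies each rule to the same current dose and platelet count and compares the results.

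**1. Escalation from 100 mg after at least 7 unchanged days** (Sections 4.1/4.2 against the Table 1 platelet rows)

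| Platelets | Sections 4.1/4.2 | Table 1 |
|---|---|---|
| 75 to < 125 | 200 mg | 150 mg, then held |
| ≥ 125 | 200 mg | 150 mg, then 200 mg after at least 7 more days |

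In the first row the gap is 200 − 150 = 50 mg, and 50/200 = 25%. It does not close by itself. At 75 to < 125 Table 1 maintains any dose of 150 mg or more, so a subject raised under Section 4.1 stays at 200 mg and one raised under Table 1 stays at 150 mg. In the second row the gap lasts at least 7 days.

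**2. Effect on relative dose intensity (RDI).** Illustrative assumptions: 24 weeks (168 days) of treatment, 100 mg on Days 1 to 7, escalation on Day 8, and platelets at 75 to < 125 throughout.

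- Planned total under Sections 4.1/4.2: 7 × 100 + 161 × 200 = 32,900 mg.
- Planned total under Table 1: 7 × 100 + 161 × 150 = 24,850 mg.
- A subject who follows Table 1 exactly has an RDI of 24,850/24,850 = 100% or 24,850/32,900 = 75.5%, depending on the plan used.
- A subject who follows Section 4.1 exactly has an RDI of 32,900/32,900 = 100% or 32,900/24,850 = 132.4%.

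**3. Restart after an interruption for platelets < 50**

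| Dose before | Step listed in Section 6.2 text | Table 1, one level lower |
|---|---|---|
| 300 mg | none listed | not a level |
| 200 mg | 100 mg (−50%) | 150 mg (−25%) |
| 150 mg | none listed | 100 mg |
| 100 mg | 50 mg (−50%) | 75 mg (−25%) |
| 75 mg | none listed | 50 mg |
| 50 mg | none listed | no level exists |

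The Section 6.2 text also allows restart at the unchanged dose, which the Table 1 row does not.

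**4. Gaps.** The 300 mg and 50 mg rows are omissions, not contradictions. Table 1 does give explicit instructions for 50 mg at platelets 50 to < 75. Only the < 50 row leaves that dose without a next step.

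**The case against.** The best defence on escalation is that Table 1 is, by its title, a guide to managing cytopenias, while Sections 4.1 and 4.2 govern initial titration, so the two never meet. That reading is reasonable, but no sentence states it, and two features tell against it. Table 1 contains increase rules whose trigger, a week on 100 mg or less without change, describes a 100 mg starter on Day 8. Section 4.1 itself sends the reader to Table 1 for raising a reduced ruxolitinib starting dose, so Table 1 is not confined to toxicity.

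On restart the defence is stronger. The 200 to 100 to 50 mg line sits under a bullet about reintroduction after an interruption for any cause, and that bullet cites Table 1. The thrombocytopenia paragraph says Table 1 applies, and a 150 mg dose is expressly allowed. What remains is that the bullet invokes both lists at once, the size of a moderate adjustment is not defined, and the two texts still differ on whether the unchanged dose may be resumed after platelets < 50.

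On the gaps, Section 6.2 requires discussion with the medical director for additional dose reductions or modifications, which gives a fallback. At platelets 75 to < 125 the maintain rule would cover 300 mg. That dose also becomes available only after the Week 25 Day 1 assessment, so it follows the scheduled Week 24 spleen scan.

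RDI is a descriptive summary, and the SAP does not say that toxicity reductions alter the planned dose. Only the escalation mismatch can therefore be shown to bear on it. The Operations Manual (Protocol Appendix I) is not part of the text examined and may add dosing detail.

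**Conclusion.** The escalation contradiction stands as written and nothing in the documents resolves it. It concerns subjects who start at 100 mg. Given the screening minimum of 100, these are broadly subjects with baseline platelets of 100 to 150. The documents do not give their share of the 230. For those whose platelets stay at 75 to < 125, the next dose is 150 mg or 200 mg depending on the passage read, and the difference persists. The restart mismatch is secondary and partly reconciled. The 300 mg and 50 mg points are gaps.

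A reader might infer that every platelet-driven reduction has two conflicting answers, a 50% or a 25% cut, and that sites following the protocol will necessarily dose differently. The documents do not support this. A reduction without interruption at platelets 50 to < 75 is governed by Table 1, and the Section 6.2 steps concern restart. Investigator judgement and consultation with the medical director also apply, so the supportable word is may.

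Nor do the documents show an effect on the primary comparison. In the earlier study M16-109, 83% of subjects had a navitoclax reduction, mainly for thrombocytopenia (Section 4.2). That suggests dose-adjustment rules will be used often, but the population and regimen differed, and the figure does not measure the effect of this inconsistency.

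**What to change.** Reconcile Protocol Sections 4.1, 4.2 and 6.2 and Table 1 so that one set of dose levels and one set of rules cover initial escalation, reduction and restart for every permitted dose, including the highest and the lowest. State whether the initial escalation falls under Table 1, and which text governs restart for each cause of interruption. In SAP Section 6.0, define the planned dose by reference to that single set. Use the same set to judge the incorrect-dose category in SAP Appendix A.

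The clinical team decides which rule applies; no dose is proposed here. The cost is a clarification letter or amendment wording plus a short SAP definition. No new data are needed and the sample size does not change.

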Navitoclax accelerates apoptosis of circulating mature platelets whether endogenous or transfused. This mechanism of toxicity differs from the thrombocytopenia caused by ruxolitinib and other conventional chemotherapy (i.e., toxicity to platelet progenitors in the bone marrow) and should, therefore, be managed according to the guidelines provided in [Table 1](#), unless previously discussed and approved with the AbbVie TA MD/SD.

Hematology samples must be collected within 24 hours prior to the first dose of study drug to determine dose of study drug, at 4 hours after the first dose of study treatment, and on Day 2 (see Activity Schedule, [Appendix D](#), and Operations Manual, Section 3.14). The investigator should consider additional hematology labs on Day 3 and/or Day 4 for subjects with a lower baseline platelet count and for subjects who experience a > 40% decrease in platelet count on Day 2 from the pre-dose platelet count. Additional hematology labs may be performed based on platelet counts as medically indicated at the investigator's discretion.

Any Grade ≥ 2 bleeding event (regardless of platelet count) will require interruption of dosing. Upon resolution of a Grade ≥ 2 bleeding event, study drug treatment may be reintroduced at the same or lower dose level (in consultation with the AbbVie TA MD/SD), provided the patient is asymptomatic with no evidence of an active bleeding.

If platelet transfusions are required in response to active bleeding, navitoclax/placebo dosing should be interrupted. It should be noted that platelet response with transfusions may not follow typical platelet kinetics of thrombocytopenia as with typical chemotherapy-induced thrombocytopenia. Procedures consistent with local institutional blood banking guidelines regarding platelet transfusions should be followed.

Platelet Transfusion Recommendations:

If platelet transfusion is deemed necessary, the treating physician should be aware that due to the rapid apoptotic effect of navitoclax on mature platelets, the increase in platelet counts post-transfusion may be lower and the duration of response may be shorter. Therefore, donor platelets collected as recently as possible prior to transfusion should be used. Additional transfusions may be necessary to achieve the desired platelet count. Post-transfusion platelet count monitoring should include:

- A platelet count obtained 10 to 60 minutes post transfusion.

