APPENDIX D. ACTIVITY SCHEDULE

The following table shows the required activities. The individual activities are described in detail in the **Operations Manual**.

Study Activities Table

Activity	Screening/ Baseline	Week 1	Week 1	Week 2	Week 3	Week 5	Week 7	Week 9	Week 13, 17, 21, 25	Q12 weeks as of Week 37	Treatment Completion Visit	30-Day Safety Visit (± 3 Days)	Post-Treatment Visits (± 3 Weeks)	Survival Follow Up
	Day -28 to Day -1	Day 1	Day 2	Day 1 (± 1 day)	Week 13, 17, 21 Day 1 (± 2 days). Week 25 Day 1 (± 3 days)	From Week 37 Day 1 (± 4 days)								
INTERVIEWS & QUESTIONNAIRES														
Informed consent	✓													
Eligibility criteria	✓													
Medical/surgical/transfusion history	✓	✓												
Alcohol and nicotine use	✓													
Adverse event assessment	✓	✓	✓	✓	✓	✓	✓	✓	✓	✓	✓	✓		
Prior/concomitant therapy/transfusion	✓	✓	✓	✓	✓	✓	✓	✓	✓	✓	✓			
Post-treatment therapy/transfusion/surgery												✓	✓	✓
MFSAF v4.0 (Daily)	✓	✓ (Daily through end of Week 36)												
EORTC QLQ-C30 v3.0		✓				✓			✓ (Week 13, 25)	✓	✓			
PROMIS Fatigue SF 7a	✓	✓				✓			✓ (Week 13, 25)	✓	✓			
EQ-5D-5L		✓				✓			✓ (Week 13, 25)	✓	✓			
PGIC									✓ (Week 13, 25)					

Activity	Screening/ Baseline	Week 1	Week 1	Week 2	Week 3	Week 5	Week 7	Week 9	Week 13, 17, 21, 25	Q12 weeks as of Week 37	Treatment Completion Visit	30-Day Safety Visit (± 3 Days)	Post-Treatment Visits (± 3 Weeks)	Survival Follow Up
	Day -28 to Day -1	Day 1	Day 2	Day 1 (± 1 day)	Week 13, 17, 21 Day 1 (± 2 days). Week 25 Day 1 (± 3 days)	From Week 37 Day 1 (± 4 days)								
PGIS	✓	✓							✓ (Week 13, 25)					
ECOG performance status	✓	✓		✓	✓	✓	✓	✓	✓	✓	✓			
Survival follow-up call (approximately every 2 months for up to 8 years)														✓
LOCAL LABS & EXAMS														
MRI (or CT scan) for spleen assessment	✓								✓ (Week 13, 25)	✓ (Week 37, 49, 73, 97)	✓		✓	
12-lead ECG	✓					✓					✓			
Vital signs: including height (Screening only), weight, BP, pulse, and body temperature	✓	✓		✓	✓	✓	✓	✓	✓	✓	✓	✓		
Physical examination including skin examination, spleen and liver measurement by palpation	✓	✓		✓	✓	✓	✓	✓	✓	✓	✓		✓	
Disease Assessment by IWG									✓ (Week 13, 25)	✓ (Week 37, 49, 73, 97)	✓		✓	
Serum/urine pregnancy test	✓	✓				✓		✓	✓ (monthly from Week 25 where a	✓ (monthly where a regulatory requirement)	✓			

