Activity	Screening/ Baseline	Week 1	Week 1	Week 2	Week 3	Week 5	Week 7	Week 9	Week 13, 17, 21, 25	Q12 weeks as of Week 37	Treatment Completion Visit	30-Day Safety Visit (± 3 Days)	Post-Treatment Visits (± 3 Weeks)	Survival Follow Up
	Day -28 to Day -1	Day 1	Day 2	Day 1 (± 1 day)	Week 13, 17, 21 Day 1 (± 2 days). Week 25 Day 1 (± 3 days)	From Week 37 Day 1 (± 4 days)								
									regulatory requirement)					
TB screening (PPD or IGRA)	✓													
Clinical chemistry, hematology, coagulation	✓	✓	✓ (hem only)	✓	✓	✓	✓	✓	✓	✓	✓		✓ (hem only)	
Lipid parameters – fasting state	✓								✓ (Week 13)					
Bone marrow biopsy and cytogenetic assessment (Screening plus standard of care) for local evaluation of disease	✓								✓ (Week 25)	✓ (Week 49, 73)	✓		✓	
Bone marrow aspirate for local evaluation of disease	✓								✓ (Week 25)	✓ (Week 49, 73)	✓		✓	
 CENTRAL LAB														
Blood samples for PK assay		✓		✓	✓	✓								
Blood for mutational profiling	✓								✓ (Week 13, 25)	✓ (Week 49, 73)	✓			
Blood for immune cell biology		✓							✓ (Week 25)	✓ (Week 49)				
Blood for PBMC		✓							✓ (Week 25)	✓ (Week 49)				

Activity	Screening/ Baseline	Week 1	Week 1	Week 2	Week 3	Week 5	Week 7	Week 9	Week 13, 17, 21, 25	Q12 weeks as of Week 37	Treatment Completion Visit	30-Day Safety Visit (± 3 Days)	Post-Treatment Visits (± 3 Weeks)	Survival Follow Up
	Day -28 to Day -1	Day 1	Day 2	Day 1 (± 1 day)	Week 13, 17, 21 Day 1 (± 2 days). Week 25 Day 1 (± 3 days)	From Week 37 Day 1 (± 4 days)								
Blood for plasma markers	✓								✓ (Week 13, 25)	✓ (Week 49)	✓			
Blood for allelic burden	✓								✓ (Week 13, 25)	✓ (Week 49, 73)	✓			
Blood for translational research	✓								✓ (Week 13, 25)	✓ (Week 49, 73)	✓			
Bone marrow biopsy (fibrosis grading/biomarker research)	✓								✓ (Week 25)	✓ (Week 49, 73)	✓		✓	
Bone marrow aspirate for mutational profiling	✓								✓ (Week 25)	✓ (Week 49, 73)	✓			
Bone marrow aspirate for allelic burden	✓								✓ (Week 25)	✓ (Week 49, 73)	✓			
Bone marrow aspirate for translational research	✓								✓ (Week 25)	✓ (Week 49, 73)	✓			
Optional Biomarker Sample: Whole Blood DNA and RNA		✓							✓ (Week 13)		✓			

Activity	Screening/ Baseline	Week 1	Week 1	Week 2	Week 3	Week 5	Week 7	Week 9	Week 13, 17, 21, 25	Q12 weeks as of Week 37	Treatment Completion Visit	30-Day Safety Visit (± 3 Days)	Post-Treatment Visits (± 3 Weeks)	Survival Follow Up

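### Table 1 does not say which row sets the ruxolitinib dose at restart after platelets fall below 50 × 10⁹/L, so a literal reading permits more than the table's own dose for the recovered count (low priority)

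*Protocol*

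**What the plan says.** All platelet counts here are in units of 10⁹/L and all ruxolitinib doses are twice daily.

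In Protocol Section 6.2, Table 1, the ruxolitinib column for platelets < 50 tells the site to interrupt per local label, with a taper possible. A separate bullet then reads: "Resume at same or lower dose once platelet counts recover" to at least 50. That bullet mentions neither the label nor the other rows.

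The rows that describe a recovered count are:
- 50 to < 75: "Reduce dose to 5 mg twice daily", with no condition on the current dose.
- 75 to < 100: "Reduce dose to 10 mg twice daily if current ruxolitinib dose" is 15 mg or more; a dose of 10 mg or less is kept.
- 100 to < 125: one level lower if the dose is 20 mg or more; 15 mg or less is kept.

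The column is headed "Ruxolitinib per approved local label". Section 6.2 says that thrombocytopenia "should, therefore, be managed according to the guidelines provided in" Table 1 unless the sponsor's medical director has approved otherwise. It also sends sites to the local label, "in addition to the dose modification guidelines provided below and in" Table 1, for dose adjustment that includes hematological toxicity. In the same < 50 row, navitoclax/placebo must restart one dose level lower.

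**The concern.** Two rows of one safety table can apply to the same patient on the same day and give different ruxolitinib doses. A subject whose count falls into the 50 to < 75 band goes to 5 mg. A subject who climbs into that band from below 50 may, on the words of the < 50 row, go back to 10, 15 or 20 mg. There is no evident reason for the second subject to receive more than the first.

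At stake are patient safety and consistent dosing. Thrombocytopenia is the primary dose-limiting toxicity of navitoclax (Protocol Section 2.2), and ruxolitinib adds to it by slowing platelet production (Section 4.2). Two sites could treat the same count differently and both be within the protocol.

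**Working it through.** The plan states no figure to reproduce. The check compares the highest restart dose that the < 50 row allows (the pre-interruption dose) with the dose that the table sets for the recovered count.

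**Inputs.** Row doses are from Table 1. Starting doses are 20 mg (platelets > 200) and 15 mg (100 to 200), from Section 4.1. Visit timing is from Appendix D, in the row "Clinical chemistry, hematology, coagulation" and the column "Q12 weeks as of Week 37".

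**Step 1: ratio of literal restart dose to table dose.**

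| Prior dose | Recovered to 50 to < 75 (table: 5 mg) | Recovered to 75 to < 100 (table: at most 10 mg) |
|---|---|---|
| 5 mg | 5/5 = 1 | no excess |
| 10 mg | 10/5 = 2 | 10/10 = 1 |
| 15 mg | 15/5 = 3 | 15/10 = 1.5 |
| 20 mg | 20/5 = 4 | 20/10 = 2 |

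At 100 to < 125 only a prior dose of 20 mg conflicts. If one level lower means 15 mg (an assumption, since Table 1 does not define ruxolitinib levels), the ratio is 20/15 = 1.33. At 125 or above there is no conflict.

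**Step 2: who is affected.** A subject stepped down to 5 mg in the 50 to < 75 band has no excess. To be interrupted while still on 10 mg, the subject must reach < 50 with no acted-on count in 50 to < 75. For 15 mg there must also be none in 75 to < 100, and for 20 mg also none in 100 to < 125. The smallest fall from the lowest count at which the table leaves the dose alone is 1 − 50/c:
- 10 mg, c = 75: more than 33.3%
- 15 mg, c = 100: more than 50%
- 20 mg, c = 125: more than 60%

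**Step 3: whether the schedule leaves room.** Scheduled hematology is at Weeks 1, 2, 3, 5, 7, 9, 13, 17, 21 and 25, then every 12 weeks from Week 37. The gaps are 4 × 7 = 28 days from Week 9 to Week 25, and 12 × 7 = 84 days after that. Assuming a constant rate of decline, the average daily fall needed is 1 − (50/c)^(1/days):

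| Prior dose (c) | Over 28 days | Over 84 days |
|---|---|---|
| 10 mg (75) | 1.44% | 0.48% |
| 15 mg (100) | 2.45% | 0.82% |
| 20 mg (125) | 3.22% | 1.08% |

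These rates show only that a fall can pass between scheduled counts. They do not say how often it will. Unscheduled local counts, which Section 6.2 leaves to the investigator, would make it rarer.

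**Step 4: where the recovered count is likely to lie.** During the interruption platelets are rechecked about every 2 to 3 days until they reach 50, and restart is allowed from that threshold. The first qualifying count can therefore readily fall in the 50 to < 75 band, where the ratio is largest.

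**The case against.** The strongest reply is that the table can be read without conflict. Its rows are keyed to the current count, so a count of 50 to < 75 calls for 5 mg whatever came before. The restart bullet sets an upper limit and does not instruct a same-dose restart, and 5 mg satisfies both rows. This stands, and a careful investigator can comply with both. However, the 50 to < 75 row speaks of reducing a dose, which presupposes a subject on drug, and the restart bullet is the only thrombocytopenia text that addresses resuming ruxolitinib. Neither row is given precedence.

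The second reply is the local label. It heads the column, and Section 6.2 invokes it for hematological toxicity. It may well cap the restart dose. Its doses are not in the documents, so this can be neither confirmed nor ruled out, and with about 26 countries uniform label wording cannot be assumed.

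The third reply is the recheck. The navitoclax/placebo step-down is a dose modification, so platelets are rechecked at about 7 days or sooner, until two consecutive values are stable. A count in a lower band then triggers that row's dose. This also stands: it should usually limit an excess to about a week, during which navitoclax/placebo is also reduced. It limits how long the excess lasts but does not set the restart dose. Sponsor approval does not set it either, because a same-dose restart is within Table 1, and consultation on dose level is only recommended. The weekly laboratory review in Section 5.5 can catch a high dose only afterwards.

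Finally, early hematology is dense (4 hours after the first dose, Day 2, then every one to two weeks to Week 9), and Section 4.2 notes that the platelet effect of navitoclax may lessen with continued dosing. Both points make the situation less likely. Neither excludes it.

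**Conclusion.** The point holds as a low-priority correction for safety and dosing consistency. Table 1 contains an unresolved conflict between rows. For a subject who reached < 50 with no acted-on count at 50 to < 75, the literal text permits 2 to 4 times the table's dose at a recovered count of 50 to < 75, and 1.5 to 2 times at 75 to < 100 (prior dose 15 or 20 mg).

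This rests on reading the restart bullet literally and on the label not already supplying a lower cap. The limit of about a week assumes that the navitoclax/placebo step-down and its recheck take place.

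A reader might infer more, in two ways. One is that the protocol directs a fourfold overdose. It does not: a same-dose restart is permitted rather than required, the 4-fold case needs a fall of more than 60% with no intermediate count acted on, and 5 mg complies with both rows. The other is that ruxolitinib exposure would differ between arms enough to affect the efficacy comparison. The documents give no frequency for the situation, so no effect on efficacy, power or type I error can be claimed.

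**What to change.** Replace the ruxolitinib restart bullet in the < 50 row with:

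> Once platelets are back to at least 50 × 10⁹/L, resume at the same or a lower dose, not exceeding the dose this table gives for the recovered platelet count where it gives one (5 mg twice daily at 50 to < 75; 10 mg twice daily at 75 to < 100), or the local label maximum if lower. The dose may later be raised per local label, up to the pre-interruption dose, as platelets recover.

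Exceptions go through the existing medical director approval in Section 6.2.

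The second sentence is needed because the cap has a real downside. More subjects would restart at 5 mg, and Table 1 has no general upward step for ruxolitinib: its increase at 125 or above covers only subjects who started below the label dose. Without a stated way back up, the cap could prolong under-dosing of the backbone drug, and Section 2.1 notes that symptoms return quickly when ruxolitinib is stopped.

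The change is to one bullet and needs no new data or patients. An amendment needs IEC/IRB approval before use (Section 8.1) across about 190 sites in about 26 countries, so this belongs in the next planned amendment and does not justify one of its own.
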